Study Patients (Investigational product, etc.)	
 ● Patients with breast cancer, who underwent neoadjuvant chemotherapy and was suggested to have near complete or complete clinical response on breast MRI will be included.
Number of Study Patients	40 (20 each for core needle biopsy and vacuum-assisted biopsy)
Vulnerable Patients	
 ● Inclusion of any vulnerable patients (minors/pregnant women, fetuses, newborns/adults with impaired cognition of consent/students, employees/inmates) will be recorded.
Study Method	
 ● Before the surgery, needle biopsy or vacuum-assisted breast biopsy will be performed, focusing on the primary tumor and the peripheral area and will be marked with a clip. Local resection will be performed subsequently. ● Accuracy of the prediction of pCR by breast MRI and multiple-core needle biopsy or vacuum-assisted breast biopsy will be determined by analysis of final pathological findings of the surgically removed breast tissue. ● Clinical pathological factors that may influence the accuracy of the prediction of pCR by breast diagnostic images and multiple-core needle biopsy or vacuum-assisted breast biopsy will be examined. ● The planned number of patients to be enrolled in this study is 40. Of these, 20 patients will receive multiple-core needle biopsy while the remaining 20 will receive vacuum-assisted breast biopsy. A comparative analysis will be done to assess which method has a better prediction rate.
Efficacy	Not applicable.

Evaluation	
Safety Evaluation	Not applicable.
Expected Effects and Results	
 Results from this study will help in accurately identifying and screening patients with breast cancer who have achieved pCR after neoadjuvant chemotherapy and hence, do not need surgery. It will allow decreases the economic, psychological, and social burdens on the patient. In addition, issues such as deformation of the breast due to surgery, side-effects arising from various surgical procedures (infection, bleeding, and wounds) and anesthesia can be avoided.

Study Protocol

1. Study Title

Prediction of pathologic complete response (pCR) by preoperative biopsy in breast cancer with complete clinical response (cCR) after neoadjuvant chemotherapy

2. Study Background and Purpose

1) Study Background

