 - In a previous study, sensitivity to residual tumors after neoadjuvant chemotherapy was measured using breast MRI was at 83%, specificity 47%, positive-predictive value (PPV) 47%, negative-predictive value (NPV) 83%, and accuracy 74%.
 - Histological examination of tumors is considered to be an important factor in improving accuracy. The accuracy of pCR prediction is determined to be acceptable when it is 90% or higher, considering that local recurrence rate is about 10% in patients undergoing surgical resection, as observed in previous studies.
 - In this study, pCR prediction results of breast magnetic resonance imaging (MRI) and biopsy (multiple-core needle biopsy and vacuum-assisted breast biopsy) will be compared with the prediction results of the breast specimens undergoing quadrantectomy involving primary tumors.
 - If residual tumors are observed in the surgical specimens, pathological factors such as the distance from the primary tumor with clipping and the occurrence of necrosis will be analyzed.
- B. To develop a basic examination technique that would allow screening of patients based on whether they need local resection or not, when making preoperative determination by pathological response.
 - The pCR after neoadjuvant chemotherapy will be determined by non-surgical method.
 - Using a RCT design, enrolled patients will be divided into two groups based on whether they received

- surgery or not.
- Follow-up with local recurrence rate will be the primary endpoint, while disease-free survival (DFS) and overall survival (OS) will be the secondary endpoints. Based on the results, patients who do not need surgical treatment will be identified.
- In this study, if the pCR can be accurately determined, it is possible to conduct further studies on the extent of surgery (local excisional biopsy with local anesthesia vs. multiple-core needle biopsy vs. segmentectomy)

3. Investigational product and medical device code name (or common name of main ingredient), amount of drug substance, formulation, etc. (including a control drug)

Not applicable.

4. Selection Criteria, Exclusion Criteria, Target Number of Patients and Basis for Calculation

1) Selection Criteria

All patients undergoing neoadjuvant chemotherapy and those who are expected to have near complete or complete clinical response immediately before surgery, as confirmed by MRI will be included. (tumor size ≤ 0.5 cm or Lesion-to-Background Signal Enhancement Ratio [L-to-B SER] ≤ 1.6).

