2) Exclusion Criteria

- Multifocality (≥ 3)
- Residual diffuse microcalcification
- Patients who drop out due to complications or cancer progression during neoadjuvant chemotherapy.
- Patients with residual tumors observed immediately before surgery, as observed by MRI and ultrasound.

3) Target number of patients and basis of calculation

The primary endpoint of this study is to perform an additional biopsy after MRI to determine if specificity was greater than 90% (one-sided test). To calculate the number of patients to meet this primary endpoint, the following assumptions were made.

※ Gold standard: biopsy after surgery

- (1) Level of significance, $\alpha = 0.05$, one-sided test
- (2) Type II error (β) is 0.20, and the test power is maintained at 80%.
- (3) The hypothesis of this study is as follows.

Null hypothesis: The specificity of MRI + biopsy is not 64% ($p \neq 0.64$).

Alternative hypothesis: The specificity of MRI + biopsy is greater than 64% ($p > 0.64$). However, a specificity of 90% is expected.

(4) Based on the results from previous studies, MRI data showed that 64% of the patients had no tumors in the actual surgical tissues. Therefore, the specificity of MRI is assumed to be 64%. In case of MRI + biopsy, specificity is expected to be 90%.

Based on this, the number of study patients was calculated using the below formula.

$$n = \frac{(z_\alpha \sqrt{p_0 q_0} + z_\beta \sqrt{p_1 q_1})^2}{\delta^2}$$

Based on the calculation, 17 patients are required to secure 80% probability of rejecting the above null hypothesis at a significance level of 5%.

At this time, 17 patients were counted using the specificity (ratio of complete response in the MRI + needle biopsy results from the patients who would show complete response in the biopsy after surgery [gold standard] results), so it would only represent the number of patients who would have complete response as a result of biopsy after surgery. Therefore, the total number of patients should be calculated by reflecting prevalence (among 100 patients suspected of complete response in our study, the ratio of actual complete response in the postoperative biopsy is 64%) and the results are as follows.

Prevalence (A)	Total number of patients (B)	Number of total study patients considering the dropout rate 10% (C)
64%	27	30

4) Study Patient Recruitment Plan

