- Multiple-core needle biopsy (14-gauge) or vacuum-assisted breast biopsy (10-gauge) will be performed. Obtaining at least five cores is recommended. Multiple-core needle biopsy will be performed at five different locations where the mass is seen before chemotherapy and in areas with the highest blood flow,

as seen in the color Doppler image or the lowest echo on B-mode ultrasound, thus indicating the highest likelihood of residual tumor. The clip inserted during the course of neoadjuvant chemotherapy will also be used as reference.

- To minimize variation while performing biopsy, two different radiologists, with at least five years of experience, will perform the biopsies at sites determined by consensus.
- Amongst the total 40 patients in this study, 20 will undergo multiple-core needle biopsy and 20 will undergo vacuum-assisted breast biopsy. The patients will be assigned alternatively. The prediction rates obtained from the two groups will be compared.
- The rate at which complete responses is achieved by neoadjuvant chemotherapy varies by breast subtype. According to the Seoul National University Hospital data, about 5% of hormone receptor-positive (HR+) breast cancers and 20% or more of Her2-positive (HER2+) or triple-negative breast cancers (TNBC) have shown complete response after neoadjuvant chemotherapy.
- When predicting complete response with breast MRI, PPV also showed high prediction rate for TNBC and non-hormone receptor expression/Her2 positive subtypes and about 45% prediction rate for luminal subtypes.

C. Determining factors that influence the accuracy of pCR prediction after neoadjuvant chemotherapy

- The accuracy of prediction of pCR by breast MRI is likely to be affected by subtypes of breast cancer and the size and location of the tumor prior to neoadjuvant chemotherapy. Thus, the clinical pathological factors that influence the accuracy of the prediction will be analyzed.
- Analysis will be performed by categorizing the tumors according to the patient's age, density of breast tissue (grade), and histological characteristics of the tumor.

2) Comparative group setting and randomization method

The patients will be alternatively assigned in a 1:1 ratio in the multiple-core needle biopsy group and vacuum-assisted breast biopsy group, such that one patient would receive multiple-core needle biopsy and the next will receive vacuum-assisted breast biopsy.

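### In a cohort of MRI responders only, MRI accuracy by factor is just the pCR rate by factor, and NPV by factor also moves with the pCR rate, so neither can show what affects the test

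*Combined protocol and SAP*

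**What the plan says.** Entry depends on the MRI result. Under Selection Criteria (Section 4.1), "those who are expected to have near complete or complete clinical response immediately before surgery, as confirmed by MRI will be included". The Exclusion Criteria (Section 4.2) remove "Patients with residual tumors observed immediately before surgery, as observed by MRI and ultrasound". Section 5.1.B reserves the biopsy for patients in whom MRI predicts a complete response.

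The factor analysis is in Section 5.1.C. Its rationale concerns MRI: "The accuracy of prediction of pCR by breast MRI is likely to be affected by subtypes of breast cancer", together with pre-treatment size and location. It concludes: "Thus, the clinical pathological factors that influence the accuracy of the prediction will be analyzed". Age, breast density and histology are added as categories. The Study Overview (Study Method) describes the same analysis more widely, as "Clinical pathological factors that may influence the accuracy of the prediction of pCR by breast diagnostic images and multiple-core needle biopsy" or vacuum-assisted biopsy. Neither place names an accuracy measure or a model, or says whether patients with and without residual tumour are to be analysed separately.

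Section 5.9 makes NPV the primary endpoint, with FNR and accuracy secondary. It does not tie any of them to the factor analysis.

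The plan reports that response differs by subtype. Section 5.1.B gives complete response of about 5% in hormone receptor-positive cancers and 20% or more in HER2-positive or triple-negative cancers. For complete response predicted by MRI it gives "about 45% prediction rate for luminal subtypes". Section 4.3 states that "among 100 patients suspected of complete response in our study, the ratio of actual complete response in the postoperative biopsy is 64" per cent.

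**The concern.** A test's accuracy can be related to patient factors only if the test result varies. Here the MRI result is the entry ticket and is the same for everyone. A factor that lowers the pCR rate will then appear to impair MRI even if MRI performs identically in all patients.

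Biopsy results do vary, so MRI plus biopsy can be evaluated. Even so, NPV and overall accuracy depend on how many patients have residual tumour as well as on how many tumours the biopsy misses.

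Two findings need to be kept apart: that the biopsy misses a larger fraction of residual tumours in a subtype, and that more patients in that subtype have residual tumour. The first calls for better sampling. The second bears on whom to select for omission of surgery. An analysis that merges them could send technique development in the wrong direction.

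**Working it through.** **Convention.** As in the plan, residual tumour is the positive condition. Sensitivity = P(test shows residual | residual) = 1 - FNR. Specificity = P(test shows no residual | pCR).

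**Plan's own figure.** Section 4.3, with p0 = 0.64, p1 = 0.90, one-sided alpha 0.05 and power 80%: n = (1.645 x 0.48 + 0.842 x 0.30)^2 / 0.26^2 = 16.06, rounded up to 17. Then 17/0.64 = 26.6, so 27, and 27/0.9 = 30. All three figures reproduce. The point does not turn on them; it uses only the 64% and the 90%.

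**Step 1: MRI alone.** Accuracy = pCR x specificity + (1 - pCR) x sensitivity. Every enrolled reading predicts response, so within the cohort specificity = 1 and sensitivity = 0, and accuracy = pCR rate. That is 64% overall and about 45% in luminal tumours, a 19-point gap that says nothing about MRI.

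**Step 2: how far the base rate alone can go.** Treat luminal and hormone receptor-positive as one group, and the plan's complete response figures as pCR rates before MRI selection (both assumptions). A predictive value of 45% at a 5% base rate implies a likelihood ratio of (0.45/0.55)/(0.05/0.95) = 15.5. The same ratio at a 20% base rate gives odds of 0.25 x 15.5 = 3.89, a predictive value of 79.5%. An identical test can thus show a gap of about 34 points.

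**Step 3: MRI plus biopsy.** Inputs: specificity 90% (Section 4.3); pCR 64% overall and 45% luminal; luminal share s of 20-40% (assumption); the same FNR in all subtypes (assumption, main value 20%).

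- pCR in other subtypes = (0.64 - 0.45s)/(1 - s): 68.8% at s = 20%, 72.1% at 30%, 76.7% at 40%.
- NPV = 0.90 pCR / [0.90 pCR + (1 - pCR) FNR]. At FNR 20%, luminal: 0.405/(0.405 + 0.110) = 78.6%. Others: 0.619/(0.619 + 0.0625) = 90.8% at s = 20%, and 0.690/(0.690 + 0.0467) = 93.7% at s = 40%.
- Error = (1 - pCR) FNR + 0.10 pCR. At FNR 20%, luminal: 0.110 + 0.045 = 15.5%. Others: 0.0625 + 0.0688 = 13.1% at s = 20%, and 0.0467 + 0.0767 = 12.3% at s = 40%. The ratio is 1.18 to 1.26.

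Varying the assumed FNR, with specificity held at 90%:

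| FNR, same in all subtypes | NPV luminal | NPV others | Error luminal | Error others |
|---|---|---|---|---|
| 50% | 59.6% | 79.8-85.5% | 32.0% | 19.3-22.5% |
| 20% | 78.6% | 90.8-93.7% | 15.5% | 12.3-13.1% |
| 10% | 88.0% | 95.2-96.7% | 10.0% | 10.0% |
| 5% | 93.6% | 97.5-98.3% | 7.3% | 8.4-8.8% |

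NPV is lower in luminal tumours in every row. The error rate is higher in luminal tumours when sensitivity is below specificity, equal when they are equal, and lower when sensitivity is above specificity.

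**Step 4: information available.** 40 x 0.64 = 25.6 pCR and 14.4 residual tumours are expected, or about 23 and 13 if 10% drop out. At FNR 20%, 14.4 x 0.20 = 2.9, so about 3 tumours would be missed.

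**The case against.** The strongest reply is that the plan does not fix a measure for Section 5.1.C. FNR is already a secondary endpoint, and nothing forbids examining it by factor. Section 2.2.A also plans, when the surgical specimen contains residual tumour, to look at distance from the clipped primary and at necrosis. That analysis is confined to residual-tumour patients and includes a factor related to sampling. This has weight: the plan does not look only at pooled accuracy. But the Section 2.2.A analysis states no comparison of missed with detected tumours and does not cover subtype. For MRI, the test named in the rationale of Section 5.1.C, no accuracy measure by factor can separate performance from the pCR rate in this cohort.

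It may also be said that near-complete responders bring some spread in MRI findings. They do, but no rule turns an enrolled reading into a prediction of residual tumour. The secondary subset in Section 5.9 (size, enhancement ratio and core count all met) narrows the cohort and does not create such a rule.

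A third objection stands. The aim is safe omission of surgery, and for that decision NPV by subtype, pCR rate included, is the relevant quantity. A lower NPV in luminal disease would be a true and useful result.

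The small number of missed tumours is also a fair objection to the remedy, though the planned analysis draws on the same 40 patients.

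**Conclusion.** The point holds for MRI accuracy, where it is exact and needs no assumption beyond the entry criteria: accuracy by factor is the pCR rate by factor. It holds for NPV of MRI plus biopsy whenever sensitivity is below 1. The size (about 79% against 91-94%) rests on the assumed common FNR of 20% and luminal share of 20-40%, with the plan's 90% specificity and its 45% and 64% figures.

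A reader might infer that any factor lowering the pCR rate will make MRI plus biopsy look less accurate, perhaps by about twofold. The documents do not support that. Ratios of 1.8 to 2.4 at FNR 20% need a specificity of 100% (luminal 0.55 x 0.20 = 11.0% against 4.7-6.2%), whereas the plan expects 90%, which gives about 1.2 to 1.3. The plan states no sensitivity for MRI plus biopsy, so the direction of the effect on overall accuracy cannot be settled from it. What can be said is that overall accuracy mixes case mix with test performance.

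The analysis is exploratory, but as worded its MRI part cannot answer its own question, so it should be changed.

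**What to change.** In Section 5.1.C, and in the matching item of the Study Overview:

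1. Retitle the MRI part *factors associated with pCR among MRI responders*, and do not describe its results as influences on MRI accuracy.
2. For MRI plus biopsy, tabulate each factor (subtype, pre-treatment size, location, age, density, histology) against FNR among patients with residual tumour in the surgical specimen and against specificity among patients with pCR. Give exact confidence intervals and label the tables exploratory.
3. Keep NPV by subtype as the quantity relevant to omitting surgery. Show it beside the pCR rate of the same subtype, and state that a difference in NPV is not by itself a difference in biopsy performance.

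The cost is a change of wording and a re-tabulation of data already to be collected. The downside is imprecision. With 3 of 14 residual tumours missed, the exact 95% (Clopper-Pearson) interval for FNR runs from 4.7% to 50.8% before any split by factor, so the FNR tables can describe but not establish which factors matter.

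### Section 5.1.C studies the effect of age on prediction accuracy through age categories with no cut point stated, which discards information and lets the choice of cut decide the result

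*Combined protocol and SAP*

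**What the plan says.** The Study Overview (Study Method) lists, as part of the work, an examination of clinicopathological factors that may affect how accurately imaging and biopsy predict pCR. Section 5.1.C is devoted to it. It opens with MRI: "The accuracy of prediction of pCR by breast MRI is likely to be affected by subtypes of breast cancer", and it also mentions tumour size and location before chemotherapy. It continues: "Thus, the clinical pathological factors that influence the accuracy of the prediction will be analyzed". The only statement of method is "Analysis will be performed by categorizing the tumors according to the patient's age, density of breast tissue (grade), and histological characteristics of the tumor".

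No age cut point, number of age groups, test, significance level or model is given. Section 5.9, on statistical analysis, does not mention the factor analysis, and nothing elsewhere provides for age to be analysed as measured.

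The number of patients is fixed: "The planned number of patients to be enrolled in this study is 40". The number of prediction errors is not stated, but two figures indicate it. Section 2.2.A sets the target: "The accuracy of pCR prediction is determined to be acceptable when it is 90% or higher". Section 4.3 says, of patients suspected of complete response at the centre, that "the ratio of actual complete response in the postoperative biopsy is 64" per cent.

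**The concern.** Age is recorded on a continuous scale. Sorting patients into age bands treats everyone within a band as alike and patients just either side of a boundary as different. In a large study the loss may be tolerable. Here it falls on a comparison that may contain only about four wrongly predicted patients.

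There is a second problem. Because no boundary is named, it can be set after the data are seen. With so few errors, moving it by one patient can carry the result across the 5% line. A reported effect of age, or its absence, could then reflect where the cut was placed.

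At stake is the credibility of a secondary product of the study, the list of factors said to affect prediction accuracy. The primary endpoint and the sample size are not affected.

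**Working it through.** **The plan's own figure.** There is no size or power statement for the factor analysis. The only calculation is for specificity in section 4.3, with p0 = 0.64 ("Therefore, the specificity of MRI is assumed to be 64" per cent), p1 = 0.90 ("In case of MRI + biopsy, specificity is expected to be 90" per cent), one-sided 5% and 80% power:

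n = (1.645 × √(0.64 × 0.36) + 0.842 × √(0.90 × 0.10))² / 0.26² = 16.06, rounded up to 17; 17 / 0.64 = 26.6, up to 27; 27 / 0.9 = 30.

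This reproduces. Ten more patients are added for the biopsy comparison, giving 40.

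**Expected errors in 40 patients.**
- MRI plus biopsy at 90% accuracy: 40 × 0.10 = 4.
- From 90% specificity instead: 40 × 0.64 × 0.10 = 2.56 errors among pCR patients, plus 40 × 0.36 × (1 − sensitivity). The total is 4.0 if sensitivity is 90% and 5.4 if it is 80% (assumed values).
- MRI alone: enrolled patients are those MRI predicts to be complete or near-complete responders, so the error rate is 1 − 0.64 = 36%, or 40 × 0.36 = 14.4.

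**How far the cut point decides the result.** Take 4 errors in 40, all in one age group of size k. The probability of that table is C(k,4)/C(40,4), with C(40,4) = 91,390. For k = 20 the mirror-image table is equally likely, so the two-sided Fisher p doubles. For the smaller k below, the opposite table is more likely than the observed one and is not added.

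| Split (all errors in the first group) | Calculation | Two-sided Fisher p |
|---|---|---|
| 20/20 | 2 × 4845 / 91,390 | 0.106 |
| 19/21 | 3876 / 91,390 | 0.042 |
| 10/30 | 210 / 91,390 | 0.002 |

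If the four errors lie in the 21 of the 19/21 split, p = (5985 + 3876) / 91,390 = 0.108. The choice of test matters too: uncorrected chi-square for the 20/20 table is 40 × (4 × 20)² / (20 × 20 × 4 × 36) = 4.44, p = 0.035.

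**Information lost.** Power was simulated with 40 patients, standard normal age, a logistic effect of age on the chance of a prediction error, and two-sided 5% tests. The effect sizes and the two-sided 5% level are assumptions; the protocol gives neither for this analysis.

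| Error rate | Odds ratio per SD | Rank test, age as measured | Fisher, median split | Uncorrected chi-square, median split |
|---|---|---|---|---|
| 10% | 2 | about 20% | 6% | 13% |
| 36% (MRI alone) | 2 | about 47% | 25% | 36% |

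Repeat runs agree within about two percentage points. In a run of 3000 trials at 10% errors, the range over effect size (rank test vs Fisher vs chi-square) was 11% vs 2.5% vs 7% at odds ratio 1.5, and 42% vs 12% vs 24% at odds ratio 3. With no age effect, the same run gave rejection rates of 4.7%, 1.5% and 4.6%. The rank test's advantage is therefore not bought with extra false positives, and part of Fisher's deficit is its conservatism.

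**The case against.** The strongest objection is that little hangs on this. The factor analysis is not among the primary or secondary endpoints in section 5.9 and has no significance level or decision rule. The sentence at issue is one general line in a translated protocol and can be read as a list of factors as much as a test specification. This stands, and it limits the weight of the point. It does not remove it: the line is the only statement of method, and it says age will be categorized.

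A second objection is that the scarcity of errors, not the scale of age, is the main limit. This also stands. With about four errors the rank test has only about 20% power at odds ratio 2. Even if all four errors fall at random within one half of the age range, it reaches 5% in only about 37.5% of arrangements. Age as measured makes better use of the data but does not make the analysis strong.

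A reader might infer something stronger: that a two-group age split cannot reach significance, so the analysis as written can only come out null. The documents do not support that. It would need a near-equal two-group split, a Fisher or Yates-corrected test, and at most four errors, none of which the protocol fixes. The 19/21 split and the uncorrected chi-square above already break it. So do five errors in a 20/20 split (2 × 15,504 / 658,008 = 0.047), and five or more errors have a 37% chance when four are expected. For MRI alone, which section 5.1.C names, about 14 errors are expected and an 11 versus 3 division gives p = 0.019.

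Nor does the protocol say that breast density grades will be treated as unordered. It only leaves open how they will be tested.

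**Conclusion.** The point holds as a minor improvement. The plan analyses age by categories without giving a boundary, test or reason. Under an assumed odds ratio of 2 per SD, a median split gives up about 7 to 14 percentage points of power at a 10% error rate (20% against 13% or 6%) and about 11 to 22 points at 36% (47% against 36% or 25%), depending on the comparator test. So there is a loss whether the prediction meant is MRI plus biopsy or MRI alone, though its size depends on the odds ratio.

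The cut-point problem rests on less: only on four errors in 40, which follows from the 90% accuracy target. The same kind of clustering, all errors in one age group, gives p from 0.106 to 0.002 as the boundary moves.

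This does not show that the planned analysis is incapable of finding an effect, and it has no bearing on the primary endpoint.

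**What to change.** In section 5.1.C, replace the sentence on categorizing with text to this effect:

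> Age will be analysed as a continuous variable, with a rank-sum test comparing the ages of correctly and incorrectly predicted patients. Breast density will be analysed as an ordered grade with an exact trend test. Age categories will be used in descriptive tables only. Nominal histological characteristics will be analysed by category. The factor analysis is exploratory.

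Naming a single test for age matters: a choice between tests would bring back the freedom that an open cut point allows.

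The cost is a few lines of text and no new data. The downside is that a rank or trend test is sensitive mainly to a broadly monotone relation. The descriptive table by age category remains available to show a departure from that.
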